6.5 Study Intervention Compliance

When participants are dosed at the site, they will receive study intervention(s) directly from the Investigator or designee, under medical supervision. The date, and time if applicable, of dose administered in the clinic will be recorded in the source documents and recorded in the electronic case report form (eCRF). The dose of study intervention and study participant identification will be confirmed at the time of dosing by a member of the study site staff other than the person administering the study intervention.

6.6 Dose Modification

Study intervention will be administered as described in [Section 6.1](#) and [Section 6.2](#) and per the schedule in the SoA ([Section 1.3](#)). Dose modification is not permitted.

6.7 Continued Access to Study Intervention After the End of the Study

There is no intervention after the end of the study (see definition in [Section 4.4](#)).

6.8 Treatment of Overdose

For this study, any dose of study intervention exceeding that specified in the protocol will be considered an overdose.

There is no specific treatment for an overdose with vaccine study intervention. If overdose occurs, the participant should be treated supportively with appropriate monitoring as necessary.

An overdose with associated AEs is recorded as the AE diagnosis/symptoms on the relevant AE modules in eCRF and on the Overdose CRF module. An overdose without associated symptoms is only reported on the Overdose CRF module. Refer to [Section 8.4.13](#) for details of AE/SAE reporting related to overdose.

6.9 Prior and Concomitant Therapy

All concomitant medications will be recorded in the source documents. Prohibited medications will additionally be recorded in the eCRF.

For SAEs and AESIs, medications (over-the-counter and prescription) used to treat the SAE or AESI will also be recorded in the eCRF along with the information listed below. Vitamins

and/or herbal supplements should not be recorded.

- Reason for use
- Dates of administration including start and end dates
- Dosage information including dose, frequency, and route

The Study Clinical Lead should be contacted if there are any questions regarding concomitant or prior therapy.

6.9.1 Permitted Concomitant Medications

- Participants may take concomitant medications prescribed by their primary care provider for management of chronic medical conditions and/or for health maintenance.
- Primary care providers or Investigators, where appropriate, should prescribe concomitant medications or treatments deemed necessary to provide full supportive care and comfort during the study.
- Participants who develop adverse events after receiving study intervention should be treated with licensed medications and interventions according to standard of care.
- The use of antipyretics and other pain medication to treat symptoms associated with study intervention administration or ongoing conditions is permitted.

Note: Prophylactic use of these medications to prevent symptoms associated with study intervention administration are not permitted. However, if a participant is taking medication for another condition, even if it may have antipyretic or pain-relieving properties, it should not be withheld prior to study vaccination.

- All routine vaccinations other than influenza or COVID-19 vaccines are permitted >28 days prior to and >28 days after the last dose of study intervention. Licensed influenza or COVID-19 vaccines are permitted beginning >14 days before and >14 days after administration of study intervention.

6.9.2 Prohibited Concomitant Medications

The following are prohibited, and the Sponsor must be notified if a participant receives any of these prohibited medications. Any use of prohibited medications must be recorded in the eCRF and reported as a protocol deviation.

The use of prohibited medications and/or vaccines does not always require a withdrawal of the participant from the study but may determine a participant's evaluability in the immunogenicity analysis set.

- Receipt of any licensed or investigational RSV and/or hMPV vaccine prior to administration of study intervention and through to completion of Visit 4.

- Participants choosing to receive a licensed and/or authorized RSV vaccine outside the study should inform the Investigator so it can be documented; all doses of RSV vaccine must be recorded.
- Participants who receive a licensed and/or authorized RSV vaccine outside the study should be encouraged to continue study conduct to be followed for safety reporting and all assessments
- Receipt of any licensed or investigational vaccine (other than licensed influenza or COVID-19 vaccines) within 28 days prior to, or receipt within 28 days after, administration of study intervention
 - Licensed influenza or COVID-19 vaccines are permitted beginning >14 days before and >14 days after administration of study intervention.
- Investigational products indicated for the treatment of RSV/hMPV
 - Note: For participants who become hospitalized with RSV or hMPV, participation in investigational treatment studies is permitted.
- Glucocorticoids at a dose of ≥ 20 mg/day of prednisone or equivalent given daily for ≥ 14 consecutive days between randomization and the participant's scheduled final visit.
 - Topical/inhaled steroids or short-term oral steroids are permitted.
- Immunoglobulins and/or any blood product within 3 months prior to administration of study intervention and through the participant's scheduled final visit.
- Other systemically administered drugs with significant immunosuppressive activity, such as azathioprine, mycophenolate, tacrolimus, cyclosporine, methotrexate, or cytotoxic chemotherapy, between randomization and the participant's scheduled final visit.

7 DISCONTINUATION OF STUDY INTERVENTION AND PARTICIPANT DISCONTINUATION/WITHDRAWAL

Discontinuation of specific sites or of the study as a whole are handled as part of [Appendix A](#).

7.1 Discontinuation of Study Intervention

Each participant will receive one dose of study intervention. An individual participant will not receive study intervention if any of the following occur in the participant in question:

- Participant withdraws consent after signing the ICF
- Participant meets any of the exclusion criteria or fails to meet all inclusion criteria for study participation (see [Section 5.1](#) and [5.2](#))

Each participant who has received study intervention will be followed for the full study period unless consent is withdrawn specifically from further study participation, or the participant is lost to follow-up.

Note that discontinuation from study intervention is *not* the same thing as a discontinuation or withdrawal from the study (see [Section 7.2](#)).

7.2 Participant Discontinuation/Withdrawal From the Study

Discontinuation of the participant from the study by the Investigator:

- A participant may be discontinued from the study at any time at the discretion of the Investigator for behavioral, compliance, or administrative reasons.

Voluntary withdrawal from the study by the participant

- A participant may withdraw from the study at any time at the participant's own request for any reason (or without providing any reason).
- A participant who wishes to withdraw from the study must be informed by the Investigator about modified follow-up options (eg, telephone contact, a contact with a relative or treating physician, or information from medical records).
- If the participant withdraws consent for disclosure of future information, the Sponsor may retain and continue to use any data collected before such a withdrawal of consent.
- If the participant withdraws from the study, the Sponsor may retain and continue to use any samples collected before such a withdrawal of consent for the purposes the participant originally consented unless the participant withdraws consent for use of samples already collected. If the participant specifically withdraws consent for any use of samples, it must be documented in the site study records by the Investigator and the Investigator must inform the Sponsor. Destruction of any samples taken and not yet tested should be carried out in line with documented sample withdrawal wishes in conjunction with what was stated in the informed consent and local regulation.

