2.3.3 Overall Benefit/Risk Conclusion

For the safety of participants, this protocol has incorporated various risk mitigation measures including appropriate inclusion and exclusion criteria (see [Sections 5.1](#) and [5.2](#)) and close monitoring of participants to minimize known and potential risks.

Taking into account the measures to minimize risks to study participants, the known and potential risks identified in association with IVX-A12 are justified by the anticipated benefits of protection from RSV/hMPV for participants who receive IVX-A12.

3 OBJECTIVES, ENDPOINTS, AND ESTIMANDS**Table 2 Objectives and Endpoints**

Objectives	Estimand Description/Endpoints
Primary Immunogenicity	
To characterize the nAb responses to RSV A in serum following vaccination with IVX-A12 or licensed RSV vaccine	
Population: Immunogenicity analysis set
 
Endpoints: RSV A nAb titers at Day 29
 
Intercurrent events: Participants who experience a protocol deviation that can interfere with an antibody response will be censored at the date of the intercurrent event.
 
Summary measures:
 
 • GMTs by vaccination group • GMFRs from baseline by vaccination group
Primary Safety	
To assess the safety of single IM vaccination with IVX-A12 or licensed RSV vaccine	
Population: Safety analysis set
 
Summary measures:
 
 • Incidence of immediate unsolicited AEs within 30 minutes of dosing • Incidence of injection site and systemic solicited ARs through 7 days post-vaccination • Incidence of unsolicited AEs through 28 days post-vaccination • Incidence of SAEs, MAAEs, and AESIs through 6 months post-vaccination
Exploratory	
To characterize the durability of the nAb responses to RSV A in serum following vaccination with IVX-A12 or licensed RSV vaccine	RSV A nAb titers through Day 181
To compare the nAb responses to RSV in serum following vaccination with IVX-A12 or licensed RSV vaccine	RSV A nAb and RSV B nAb titers through Day 181
To compare the nAb responses to hMPV in serum following vaccination with IVX-A12 or licensed RSV vaccine	hMPV A nAb and hMPV B nAb titers through Day 181
To evaluate CMI	Immune responses using functional and/or phenotypic profiling methods
To assess additional immune responses	Other exploratory assays for humoral or cellular immune responses may be performed based upon emerging safety, efficacy, immunobridging, and immunogenicity data

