3.3 Analysis Populations

The following populations are defined (Table 2):

Table 2 Populations for Analysis

Population/analysis set	Description
Safety analysis set (SAF)	All randomized participants who receive study intervention, irrespective of their protocol adherence and continued participation in the study.

Table 2 **Populations for Analysis**

Population/analysis set	Description
	
Participants who withdraw consent to participate in the study will be included up to the date of their study withdrawal. Participants will be classified according to the study intervention they actually received.
 
The SAF is to be used for safety analyses.

Immunogenicity analysis set (IAS)	
All participants in the SAF who have no important protocol deviations judged to have the potential to interfere with the generation or interpretation of an immune response and have baseline and at least one post-baseline immunogenicity samples collected. Participants will be classified according to the study intervention they actually received.
 
The IAS is to be used for the analysis of immunogenicity endpoints.

In addition to the analysis sets defined above, summaries of participant disposition and participants not randomized will be performed in a Screened set, including all participants who have provided informed consent.

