4.6.2.2 Presentations

All AEs will be listed for each participant.

An overall summary of safety will be presented, including the number and percentage of participants for each category, by study period. The denominator for calculation of percentages for adverse events will be the number of participants in the safety analysis set, who are still ongoing in the study at the beginning of the corresponding study period. The denominator for the calculation of percentages for solicited adverse reactions will be the number of participants who provided a response in the eDiary. Should a participant experience multiple events within a category, the participant will be counted only once for that category, in the category of their most severe or related event (where applicable). The overall summary of safety will be reproduced for each age subgroup category.

Event categories included in the overall summary are as follows:

- Study period: Day 1 to Day 29:
 - Unsolicited Immediate AE
 - Unsolicited immediate related AE
 - Unsolicited immediate severe AE
 - Unsolicited immediate related severe AE
 - Solicited AR
 - Solicited injection site AR
 - Solicited systemic AR
 - Unsolicited AE
 - Unsolicited related AE
 - Unsolicited severe AE
 - Unsolicited severe related AE
 - Unsolicited non-serious AE
 - Unsolicited related non-serious AE
 - SAE
 - Related SAE
 - Death
 - AE leading to study discontinuation
 - MAAE

- Related MAAE
- AESI
 - Related AESI
- Study period: From Day 30 to Day 181
 - SAE
 - Related SAE
 - Death
 - AE leading to study discontinuation
 - MAAE
 - Related MAAE
 - AESI
 - Related AESI
- Study period: From Day 1 to Day 181
 - SAE
 - Related SAE
 - Death
 - AE leading to study discontinuation
 - MAAE
 - Related MAAE
 - AESI
 - Related AESI

If there are at least 10 total events in an AE category (excluding ARs), that category will be presented in a summary by SOC and PT. Summaries by SOC and PT will be based on the study period used for reporting of the AE category. For example, unsolicited AEs would be summarized from Day 1 to Day 29, while SAEs would be summarized from Day 1 to Day 181. Participants with multiple occurrences are counted once per SOC and PT regardless of the number of occurrences. Unsolicited AEs by decreasing frequency on PT, based on the total across vaccine groups, will also be summarized from Day 1 to Day 29.

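### Protocol 7.1 and 7.2 conflict on whether a dosed participant can be discontinued by the investigator, and 7.2 states no continued SAE/MAAE/AESI follow-up for that route

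*Protocol*

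**What the plan says.** Protocol 7.1 states that each participant who has been dosed "will be followed for the full study period unless consent is withdrawn specifically from further study participation, or the participant is lost to follow-up". It then notes that stopping study intervention is different from leaving the study, and refers to 7.2.

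Protocol 7.2 has two parts. The first covers investigator-initiated removal: "A participant may be discontinued from the study at any time at the discretion of the Investigator for behavioral, compliance, or administrative reasons". It does not exempt dosed participants, does not refer back to 7.1, and says nothing about safety follow-up afterwards. The second part covers voluntary withdrawal, and only there does follow-up appear: "A participant who wishes to withdraw from the study must be informed by the Investigator about modified follow-up options", with telephone contact, contact with a relative or treating physician, and medical records as examples.

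Protocol Section 3 (Table 2) lists this among the primary safety measures: "Incidence of SAEs, MAAEs, and AESIs through 6 months post-vaccination". Under Protocol 8.4.1, these events are recorded up to and including the last study visit. The Schedule of Activities has no visit between Day 29 and Day 181.

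SAP 3.3 keeps dosed participants in the safety analysis set "irrespective of their protocol adherence and continued participation in the study". SAP 4.6.2.2 sets the denominator for adverse event percentages as "the number of participants in the safety analysis set, who are still ongoing in the study at the beginning of the corresponding study period".

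**The concern.** Section 7.1 reads as a closed list of two exceptions, and 7.2 opens a third at the investigator's discretion. A site that uses 7.2 after dosing departs from 7.1, and a site that follows 7.1 cannot use 7.2 for a dosed participant.

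What is at stake is the six-month safety endpoint. Each participant receives a single dose, so removal after Day 1 changes no treatment, but it can end the recording of later SAEs, MAAEs and AESIs. Because no visit falls between Day 29 and Day 181, someone removed soon after Day 29 may lose nearly all of the later ascertainment. The planned percentages make no allowance for this: neither document plans a person-time, time-to-event or other follow-up-adjusted incidence.

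**Working it through.** The main check is textual. The arithmetic only shows scale, because the documents give no figure on this point to reproduce.

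**1. Ways out of follow-up after dosing**

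| Route | Allowed by 7.1? | Allowed by 7.2? | Continued safety follow-up stated? |
|---|---|---|---|
| Consent withdrawn | Yes | Yes | Yes, modified options (7.2) |
| Lost to follow-up | Yes | Handled in 7.3 | Contact attempts and vital status (7.3) |
| Investigator decision (behavioral, compliance, administrative) | No | Yes | None stated |

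Only the third row is inconsistent, and only that row has no follow-up provision.

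**2. Treatment in the SAP percentages**

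- Day 1-181: everyone dosed is ongoing at the start, so a person removed later stays in the denominator. Any event recorded from Day 1 to removal counts. Without one, the person counts as having no event.
- Day 30-181: a person still in the study when this period begins stays in the denominator. Only an event recorded between Day 30 and removal counts.
- A person removed before Day 30 drops out of the Day 30-181 denominator but stays in the Day 1-181 denominator.

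The same rule applies to voluntary withdrawal and loss to follow-up.

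**3. Illustration of size**

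Inputs:
- Group size n = 70 (Protocol 4.1: about 140 randomized 1:1).
- Number removed by the investigator after dosing, k = 1 to 4. Assumed.
- Chance of a first MAAE after removal that goes unrecorded, q = 20% to 40%. Assumed.

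Understatement of the group's incidence = k × q / n.

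- Low end: 1 × 0.20 / 70 = 0.0029, or 0.3 percentage points.
- High end: 4 × 0.40 / 70 = 0.0229, or 2.3 percentage points.
- One missed SAE or AESI: 1 / 70 = 0.0143, or 1.4 percentage points.

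**4. Comparison with the study's precision**

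- An observed 14/70 (20%) has an exact 95% CI of 11.4% to 31.3%, so 2.3 points lies well inside the sampling error.
- With no events observed, the one-sided 97.5% upper limit is 1 − 0.025^(1/n). This is 5.13% for n = 70 and 5.44% for n = 66, the number fully followed if four were removed.

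**The case against.** The strongest reply is that the two sections can be read as a general rule and a specific one. The 7.1 sentence sits under discontinuation of intervention, and its closing note refers to 7.2. Section 7.3 also has the site ascertain whether the participant should continue, which fits a decision made by the site. This softens the conflict without removing it: the cross-reference does not say that 7.2 limits the follow-up promised in 7.1.

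Several further points stand and limit the finding.

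- A reader might infer that lost data is the only effect of removal. It is not: removal also ends the remaining clinic visits and blood draws, which may serve a practical purpose.
- A reader might blame 7.2 for the no-event counting. That comes from the SAP denominator rule, which applies to every early exit.
- A reader might suspect that sicker or frailer participants would be removed selectively, or more often in one group. The documents do not support this. Entry requires medical stability and the ability to comply, people judged unlikely to comply are excluded, and investigators involved in treatment or evaluation are blinded.
- Safeguards exist. The SAP tabulates withdrawals with reasons (4.1.1.2) and summarizes duration of follow-up (4.1.10). Protocol 7.3 seeks vital status, and 8.4.1 asks for suspected related SAEs that occur after the study ends. These make a loss visible, or catch deaths and some related SAEs. They do not replace prospective collection of SAEs, MAAEs and AESIs, and they do not adjust the percentages.
- The study is descriptive, so no decision rule depends on these incidences.

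**Conclusion.** The inconsistency holds on the text. Section 7.1 names two exceptions to full follow-up of dosed participants; 7.2 permits a third and states no continued safety follow-up for it. A dosed participant removed this way after Day 29 can go unobserved for SAEs, MAAEs and AESIs while remaining in both the Day 1-181 and Day 30-181 denominators.

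The likely numerical effect is small: about 0.3 to 2.3 percentage points in the affected group, resting wholly on the assumed removals and MAAE risk. It is more noticeable for a rare AESI, where one missed case could turn one observed event into none. How often investigators would use this route is unknown. The point is worth acting on because it touches a primary safety endpoint and is cheap to close; the documents do not show that the safety results would be seriously biased.

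**What to change.** Reconcile Protocol 7.1 and 7.2. One added sentence in 7.2 would do it: a dosed participant whose visits the investigator ends for behavioral, compliance or administrative reasons remains in SAE, MAAE and AESI data collection to Day 181, through the modified follow-up options already listed there, unless consent is withdrawn or the participant is lost to follow-up. A matching cross-reference in 7.1 would make the two sections agree. The investigator could still end clinic visits and blood draws.

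The cost is the wording change and a few extra telephone or record contacts. The change does not alter the SAP denominator rule, which would still apply to participants who withdraw consent or are lost.

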7.3 Lost to Follow-up

A participant will be considered lost to follow-up if the participant repeatedly fails to return for scheduled visits and is unable to be contacted by the study site.

The following actions must be taken if a participant fails to return to the study site for a required study visit:

- The site must attempt to contact the participant and reschedule the missed visit as soon as possible. The participant should be counselled on the importance of maintaining the assigned visit schedule. At this time ascertain whether the participant should or wishes to or continue in the study.
- Before a participant is deemed lost to follow-up, the Investigator or designee must make every effort to regain contact with the participant (where possible, 3 telephone calls, texts,

emails, and if necessary, a certified letter to the participant's last known mailing address or local equivalent methods). These contact attempts should be documented in the participant's medical record.

- Should the participant continue to be unreachable, the participant will be considered to have been lost to follow-up.
- Site personnel, or an independent third party, will attempt to collect the vital status of the participant within legal and ethical boundaries for all participants randomized, including those who did not get study intervention. Public sources may be searched for vital status information. If vital status is determined as deceased, this will be documented, and the participant will not be considered lost to follow-up. Sponsor personnel will not be involved in any attempts to collect vital status information.

